### Abstract

Modification on 6/20/16 shown in blue

The sympathetic nervous system provides tonic excitatory input mediated by adrenergic  $\alpha_1$  receptors to the internal anal sphincter. Defecatory disorders (DD) are attributed to inadequate rectal propulsive forces and/or impaired anal/pelvic floor relaxation during defecation. Anecdotally, many patients with DD have anxiety, but the effects of anxiety on anal sphincter pressures are unknown. DD are ideally managed by pelvic floor retraining (biofeedback therapy). However, a majority of patients with DD do not have access to biofeedback therapy and at best, 70% of patients respond to biofeedback therapy. There are no pharmacological options for DD.

This proposal will assess the contribution of adrenergic  $\alpha_1$  receptors and separately anxiety/relaxation to anal pressures in healthy and DD. The major objectives are to (1) study the effects of adrenergic  $\alpha_{1A}$  receptor antagonists on anal resting pressure, with the intent of developing pharmacological approaches to manage DD in future, (2) evaluate the effects of anxiety and mental relaxation on anal pressures, and (3) compare rectal compliance in DD and healthy subjects. Our overall hypothesis is that anxiety increases while mental relaxation reduces anal resting pressure via  $\alpha_1$  adrenoreceptor-mediated increased and reduced sympathetic tone respectively. The specific aims of this study are to evaluate the following hypotheses in healthy subjects and patients with DD: (i)  $\alpha_1$  receptors contribute to anal resting pressure but not the squeeze pressure increment; (ii) Mental stress will increase anal resting but not squeeze pressure via  $\alpha_1$  adrenoreceptors; (iii) Mental relaxation will reduce anal resting pressure via  $\alpha_1$  adrenoreceptors; hence the  $\alpha_1$  adrenoreceptor antagonist will attenuate the reduction in anal resting pressure resulting from mental relaxation; (iv) Rectal compliance is higher and the contractile response to sinusoidal oscillation is lower in DD than in healthy people; and (v) Alfuzosin will improve bowel symptoms in chronic constipation.

Anal resting and squeeze pressures will be evaluated at baseline, after randomization to the highly selective  $\alpha_1$  adrenoreceptor antagonist alfuzosin (2.5 mg) or

placebo and finally after randomization to active stress or mental relaxation in 36 healthy women and 36 female patients with defecatory disorders. Thereafter, bowel habits will be recorded at baseline (2 weeks) then during treatment with placebo or alfuzosin ER (Uroxatral™ 10 mg daily) for 2 weeks. The most significant anticipated findings are that alfuzosin and mental relaxation will reduce anal resting pressures, thereby providing additional options for patients with DD.

Finally, rectal contraction contributes to the desire to defecate. There is limited evidence, more in adolescents than in adults, that chronic constipation is associated with increased rectal compliance. Increased rectal compliance is associated with rectal hyposensitivity. In children and adolescents, increased rectal compliance is associated with severe symptoms but does not predict treatment failure. However, it is unclear if increased rectal compliance causes or is consequent to chronic constipation or if increased rectal compliance reflects reduced rectal contractile response to distention. We now propose to explore this question by using approaches that we have extensively utilized to evaluate rectal pressure-volume relationships in fecal incontinence i.e., distention with a barostat and separately with sinusoidal oscillation.

Psychological factors such as stress or depression are known to influence the natural history of chronic gastrointestinal illnesses such as inflammatory bowel disease (IBD) [15] and irritable bowel syndrome (IBS) [16] via the gut-brain axis. These conditions, and also constipation are also associated with dysbiosis. [17] Furthermore, the gut microbiota-brain axis appears to be bidirectional.[18] It is thus important to also evaluate the gut microbial profile in patients and controls to identify potential interactions between gut microbiota and

the response to stress, in health and in constipation. We propose to assess this using 16s rRNA analysis of stool samples.

This study will evaluate the following specific aims in healthy subjects and in patients with defecatory disorders:

- 1) To assess the effects of a highly-selective  $\alpha_{1A}$  receptor antagonist alfuzosin on anal resting pressure, squeeze increment, and rectoanal gradient during simulated evacuation. Our hypothesis is that  $\alpha_1$  receptors contribute to anal resting pressure but not the squeeze pressure increment in healthy people and defecatory disorders.
- 2) To study the effects of mental stress on anal resting and squeeze pressures via  $\alpha_1$  adrenoreceptors. Our hypothesis is that mental stress will increase anal resting but not squeeze pressure via  $\alpha_1$  adrenoreceptors in healthy people and defecatory disorders.
- 3) To evaluate the effects of active mental relaxation on anal resting and squeeze pressures. Our hypotheses is that mental relaxation will reduce anal resting pressure via  $\alpha_1$  adrenoreceptors; hence the  $\alpha_1$  adrenoreceptor antagonist will attenuate the reduction in anal resting pressure resulting from mental relaxation in healthy people and defecatory disorders.
- 4) To compare rectal compliance and the response to sinusoidal oscillation. Our hypotheses are that rectal compliance is higher and the contractile response to sinusoidal oscillation is lower in defecatory disorders than in healthy people.
- 5) To explore the effects alfuzosin on bowel symptoms in patients with chronic constipation. Our hypotheses are that alfuzosin will improve bowel symptoms in chronic constipation.

**6) To evaluate the role of microbiota in the relationship between stress/relaxation and defecatory mechanisms. Our hypothesis is that the susceptibility to stress is associated with differences in fecal microbiota. B. Research Design and Methods**

This study comprises 2 parts. Part A will compare the effects of oral alfuzosin (IR 2.5 mg) and placebo on anorectal functions on 1 day in all subjects (controls and patients). Part B will compare the effects of oral alfuzosin ( 10 mg ER) and placebo on bowel habits in constipated patients (but not in healthy subjects). 36 healthy women and 36 women with defecatory disorders will be enrolled in this study. This protocol is limited to women only because the vast majority of patients with constipation and defecatory disorders in our practice are women.

1. Human subjects.

- a) Inclusion Criteria for Controls (Part A only)
  - i. Healthy women volunteers aged 18-80 years
  - ii. Able to provide written informed consent before participating in the study

- iii. Able to communicate adequately with the investigator and to comply with the requirements for the entire study.

b) Inclusion Criteria for Patients (women aged 18-80 years) (Parts A and B)

- i. Constipation. Women with chronic constipation for 1 year with any 2 or more of the following symptoms for 3 months or longer, i.e. <3 bowel motions/week, straining  $\geq 25\%$  of time, hard or lumpy stools  $\geq 25\%$  of time, incomplete evacuation  $\geq \square 25\%$  of time, feeling of anorectal blockage  $\geq 25\%$  of time.
- ii. Able to provide written informed consent before participating in the study
- iii. Able to communicate adequately with the investigator and to comply with the requirements for the entire study.

c) Exclusion Criteria for Controls; Items indicated with an asterisk (\*) are also exclusion criteria for patients

- i. Clinical evidence of significant cardiovascular, respiratory, renal, hepatic, gastrointestinal, hematological, neurological, psychiatric or other disease that may interfere with the objectives of the study and/or pose safety concerns.\*
- ii. Current symptomatic orthostatic hypotension or history of hypotensive response as defined by a reduction of  $\geq 30$  mmHg in systolic or  $\geq 20$  mmHg in diastolic BP.\*
- iii. Current symptoms of a functional gastrointestinal disorder assessed by questionnaire
- iv. Putative risk factors for pelvic floor trauma, i.e. six or more vaginal deliveries, birthweight >4500gms (macrosomia), or known 4th degree perineal tear
- v. Inability to withdraw medications prior to the baseline period and throughout the study (except as protocol defined rescue medications):
  - Medications that substantially alter GI transit \* including laxatives, magnesium and aluminum containing antacids, prokinetics, erythromycin, narcotics, anti-cholinergics, tricyclic antidepressants, SNRI and newer antidepressants
  - Selective serotonin reuptake inhibitor (SSRI) antidepressants are permissible at low, stable doses. All medications shall be reviewed and dis/approved by the principal investigator on a case by case basis. \*
  - Potent Cyp 3A4 inhibitors such as ketoconazole, itraconazole and ritonavir, nitrates and phosphodiesterase inhibitors \*

NOTE: stable doses of thyroid replacement, estrogen replacement, low dose aspirin for cardioprotection, and birth control (but with adequate backup contraception as drug-interactions with birth control have not been conducted) are permissible. \*
- vi. Stable dose of thyroxine will be permitted \*
- vii. Prolonged Q-Tc interval > 500 msec on ECG within the last three months\*
- viii. Estimated glomerular filtration rate (eGFR) < 60 mL/minute. \* Based on guidelines and recommendations from the National Kidney Disease Education Program (NKDEP) of the National Institutes of Health (NIH) and the Kidney Disease Outcomes Quality Initiative (KDOQI) of the National Kidney Foundation, the an eGFR using the Modification of Diet in Renal Disease (MDRD) Study

equation is more accurate than a creatinine clearance calculated from serum and urine measurements. The formula is  $eGFR (mL/min/1.73 m^2) = 175 \times (Scr)^{-1.154} \times (Age)^{-0.203} \times (0.742 \text{ if female}) \times (1.210 \text{ if African American})$ . Based on our extensive experience in clinical practice and research studies, it is anticipated that all potentially eligible participants will have normal serum creatinine.

- ix. History of allergies to  $\alpha 1$  adrenoreceptor antagonist \*
  - x. Active rectal inflammation, cancer; perianal sepsis; history of pelvic radiation, rectosigmoid surgery or inflammatory bowel disease\*
  - xi. Pregnant women, prisoners and institutionalized individuals\*
  - xii. Persons with a latex allergy.
2. Overall experimental design. Study Assessments are shown in Table 1. During the screening visit, a clinical assessment, a medical history and physical exam, including height, weight and "vital signs" (blood pressure, temperature, heart and breathing rates), Draw a blood sample, and test urine for pregnancy if you are a female able to become pregnant, along with, questionnaires (bowel questionnaire, Hospital Anxiety and Depression Scale , a health-status questionnaire ), screening laboratory tests to exclude renal insufficiency, an ECG and a urine pregnancy test if necessary, will be completed.

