- a) Anorectal sensorimotor functions. After rectal cleansing with 1-2 sodium phosphate (Fleets®, C.B. Fleet, Lynchburg, VA) enemas, anorectal resting and squeeze pressures and rectal compliance and sensation will be evaluated before and after randomization to alfuzosin (2.5 mg oral) or placebo (Figure 1) in the Charlton 7 CRU. During each epoch (i.e., baseline or drug), pressures will be evaluated before and after patients are randomized to one of 6 sequences (orders) of 3 interventions (i.e., 2 stressors and active relaxation). The same stressor/relaxation sequence will be applied during pre-drug and post drug epochs. Anorectal assessments, which will be performed with standard techniques, include:
- Anal resting and squeeze pressures using high resolution manometry, similar to the procedure employed in the clinical lab and in recent studies;
  - Rectal compliance and sensation using a barostat/ polyethylene balloon. A conditioning distention from 0-40 mmHg in 4 mm steps at 15 second intervals will be performed. Ten minutes thereafter, the balloon will be distended from 0-44 mmHg or maximum tolerated pressure in 4 mmHg steps; sensory thresholds for first sensation, desire to defecate, and urgency will be recorded
  - Rectal ramp distention. Because the contractile response to distention is influenced by the rate of distention, a ramp distention to 200 mL over 1 minute will be performed; this will be sustained for 2 minutes. While (ii) is useful for characterizing quasi-static pressure-volume relationships representing colonic tone, ramp distentions can uncover the active contractile response to distention.
  - Rectal sinusoidal oscillation will be performed at 5 cpm for 20 minutes after distention to 125 mL. This paradigm is more sensitive than barostat-driven distentions for uncovering increased rectal stiffness in fecal incontinence but has not been evaluated in constipation

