**Figure 1. Experimental Design for Anorectal Study.** During the stress/relaxation epoch, subjects will receive 2 stress and 1 relaxation intervention in randomized order. The duration of this epoch includes two 10 minute rest periods between the 3 interventions. The manometry catheter will be removed and limited ambulation will be permitted while we are waiting for drug concentrations to increase. Combined, this wait period and the second equilibration period are 70 minutes long, which is within the range of  $t_{max}$  for alfuzosin (1.1 – 1.5 hours). PAT = peripheral arterial tonometry

- v. Rectal balloon expulsion will also be assessed in the seated position to confirm presence (or absence) of an evacuation disorder.
- b) Mental stressors and relaxation method. The mental stress testing protocol will be administered under the supervision of a licensed clinical psychologist who is familiar with these tests and routinely administers the same. Two stress interventions and a relaxation protocol will be provided in randomized order with 10-minute equilibration periods. Two different mental stress tasks of 6-minute duration will be performed. Each test is designed to address a different mental skill set. This was designed specifically to prevent mental fatigue and keep subjects motivated. All tasks will have intra-test levels of varying difficulty and will be externally paced, with the goal of stressing subjects as much as tolerated as judged by the psychologist administering the tests. It is known that external task pacing accentuates the induced mental stress. The aim is to keep subjects engaged and focused. The tasks, which will be performed in randomized order are as follows:
- i. A computerized version of the Stroop word-color conflict. Stroop word-color conflict test consists of three colored words (red, blue, and green) displayed in random order on a computer screen. Each word could appear in either its own color (visually concordant), or in one of the other 2 colors (visually discordant). The subject's task will be to enunciate the color of the word, not the actual word itself. A rectangular box will surround the stimulus color-word, and this task will also be externally paced, with the subject having to keep pace with the advancing box.
  - ii. Number subtraction of increasing difficulty (1 digit from 2 digits up to 3 digits from 3 digits) testing math skills.

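### The latex-allergy exclusion carries no asterisk, so as written it protects controls but not patients, who have the same anorectal procedures

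*Combined protocol and SAP*

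**What the plan says.** Section B.1.c holds the only exclusion list in the protocol. Its heading begins "Exclusion Criteria for Controls; Items indicated with an asterisk" and goes on to say that items so marked "are also exclusion criteria for patients". An unmarked item therefore applies to controls alone.

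Item xii, the last in the list, reads "Persons with a latex allergy" and is unmarked. The patient inclusion criteria in B.1.b do not mention latex, and the word occurs nowhere else in the documents.

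The opening of section B says that Part A compares alfuzosin and "placebo on anorectal functions on 1 day in all subjects (controls and patients"). Section B.3.a describes one set of anorectal procedures and makes no distinction by group.

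**The concern.** Latex allergy matters because of what a participant is exposed to, and in Part A the exposure is the same for patients and controls. An exclusion that applies to one group only would need a reason tied to that group, and none is given.

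What is at stake is safety at enrolment. Someone checking eligibility item by item would find that latex allergy does not exclude a patient. If any catheter, balloon or supply contains latex, the written criteria then leave the patient's protection to individual judgment. Sections C.1 and C.2.a rest subject safety partly on enrolling only people who meet the pre-defined criteria, so a gap in those criteria matters. The trial's inference is not affected.

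**Working it through.** The main check is a reading of the list, and the plan has no figure of its own to reproduce.

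**Step 1: apply the asterisk rule to every item in B.1.c.**

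| Item | Subject | Asterisk | Applies to patients |
|---|---|---|---|
| i | Significant disease, general safety | Yes | Yes |
| ii | Orthostatic hypotension | Yes | Yes |
| iii | Functional GI symptoms | No | No |
| iv | Pelvic floor trauma risk | No | No |
| v | Medications (sub-items and note) | Yes | Yes |
| vi | Thyroxine (a permission) | Yes | Yes |
| vii | QTc | Yes | Yes |
| viii | eGFR | Yes | Yes |
| ix | Allergy to the drug class | Yes | Yes |
| x | Rectal disease, radiation, surgery | Yes | Yes |
| xi | Pregnancy, prisoners, institutionalized | Yes | Yes |
| xii | Latex allergy | No | No |

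Three items are unmarked: iii, iv and xii.

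**Step 2: look for a control-only reason for each unmarked item.**

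- Item iii cannot sensibly apply to patients, who are enrolled because of constipation symptoms.
- Item iv plausibly keeps the reference group free of pelvic floor injury.
- Item xii has no such reason. It concerns materials, not what makes a control normal.

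**Step 3: compare exposure.** Section B.3.a lists manometry, barostat distention, ramp distention, sinusoidal oscillation and balloon expulsion for all Part A subjects. The one material named is in "Rectal compliance and sensation using a barostat/ polyethylene balloon". For the expulsion test the protocol says "Rectal balloon expulsion will also be assessed in the seated position" without naming the balloon's material, and the catheter's material is not given either. Latex exposure is therefore neither shown nor ruled out.

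**Step 4: see whether another item closes the gap.** Item i, which is asterisked, reaches "other disease that may interfere with the objectives of the study and/or pose safety concerns". It turns on judgment and does not name allergy. The list also gives drug allergy its own asterisked entry, item ix ("History of allergies to" the drug class), so the authors did not leave that allergy to item i.

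**Step 5: illustrate the size.** With *n* = 36 patients (section B) and an assumed prevalence *p*, the expected number of latex-allergic women is *np*, and the chance of at least one is 1 − (1 − *p*)^*n*. The documents give no value for *p*.

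| Assumed *p* | Expected number, 36*p* | Chance of at least one, 1 − (1 − *p*)^36 |
|---|---|---|
| 0 | 0 | 0 |
| 0.005 | 0.18 | 0.165 |
| 0.01 | 0.36 | 0.304 |
| 0.03 | 1.08 | 0.666 |

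These figures count allergic women among the patients. They assume that screening removes none of them, and they say nothing about how many would be exposed or harmed.

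**The case against.** The strongest reply is that no hazard is shown. The only named balloon material is polyethylene, and nothing in the documents says that a catheter, balloon or glove contains latex. That stands, and it is why the size is given as unknown and possibly zero. It does not explain the asymmetry. If there is a possible exposure, patients need the same protection; if there is none, the item excludes controls needlessly.

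Other safeguards also narrow the gap in practice. Every subject has a medical history, a physical examination and an eligibility review, trained staff run the procedures, and an investigator could reasonably treat a reported latex allergy as a safety concern under item i. This stands as mitigation, but it does not correct the written rule.

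The asterisks are used loosely. They mark permissions such as item vi, and the stem of item v has none while its sub-items do. A missing mark is therefore weak evidence that anyone meant to enrol latex-allergic patients. This is fair, and it supports reading the omission as a slip of drafting and not as a deliberate design choice.

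Finally, the mark could have been lost when the text was read from the PDF. That is unlikely, since the asterisks on items ix to xi, directly above, survived. A look at the source page would settle it.

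**Conclusion.** The concern holds. Under the list's own rule, latex allergy excludes controls and not patients, although both groups have the same Part A procedures and no reason for the difference is evident. It is most likely a drafting slip, but it sits in an operative eligibility rule.

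The consequence is limited to safety, and its size cannot be fixed from the documents. It is nil if no device or supply contains latex. The illustrative 0.2 to 1.1 latex-allergic women expected among 36 patients rests wholly on the assumed prevalence of 0.5% to 3%, and the case for the change does not depend on it. The conclusion does depend on the asterisk being absent from the source document as well as from the extracted text.

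**What to change.** Add the asterisk to item xii in section B.1.c by amendment, so that latex allergy excludes patients as well as controls.

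The change is one character. It does not touch randomization, sample size, power or analysis. Its only cost is the possible loss of a latex-allergic patient, about 0 to 1 of 36 under the assumed prevalences.

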**THE REST OF THIS PAGE IS INTENTIONALLY BLANK**

**Table 1. Schedule for Study Assessments and Monitoring**

[figure not shown]
	Screening	Acute Study	Bowel Symptoms (Alfuzosin – ER 10 mg)			
	Days –30 to 1	Day 1	Baseline Period (Days 3-16)		Treatment Period (Days 17-30)	
Procedure			Daily	Other	Daily	Other
Informed consent	X					
Review eligibility	X					
Physical examination	X					
Concomitant medication review	X	X				
Vital signs, weight	X	X 				
Serum creatinine, urine pregnancy test, ECG (12-lead)	X 					
Stool sample	X 			X 		
Anorectal study		X				
Randomization to treatment		X				
Study treatment administration		X				X 
Adverse event assessment		X		X 		X 
Stool diary (Appendix 1)			X		X	
Abdominal pain (Appendix 2)			X		X	
Global assessments (relief, severity) (Appendix 3)				Weekly		Weekly
Global assessment – satisfaction with treatment, (Appendix 4)	X			X (day 17)		X (day 31)
Other abdominal symptoms (Appendix 5)				Weekly		Weekly
Telephone contact				X  (q3-5 days)		X  (q3-5 days)

1. During the acute study, heart rate and blood pressure will be recorded at hourly intervals. Height (cm) and weight (kg) will be recorded at the screening visit but not on Day 1.
2. Urine pregnancy test to be performed for women of childbearing potential within 2 weeks of Day 1. Serum creatinine and ECG (12-lead) to have been done within three months of Day 1.
3. A single stool sample can be collected either before the acute study visit, or 3 days after the acute study visit, but before the treatment period.

4. Patients will be treated with placebo or alfuzosin ER (10 mg) once daily during this phase. While the protocol is planned for the treatment period to follow directly the baseline period, if needed for scheduling, there can be up to a 5-day interval between the baseline and treatment period.
5. Patients will be contacted by telephone every ~3-5 days between clinic visits to address questions, ascertain side effects and remind subjects to complete diaries. The final phone call will be within 5 days after completing the treatment period. Subjects will be asked to return unused medication by mail.

3. Experimental procedures. Items a-d below exclusively pertain to Part A,
- a) Anorectal sensorimotor functions. After rectal cleansing with 1-2 sodium phosphate (Fleets®, C.B. Fleet, Lynchburg, VA) enemas, anorectal resting and squeeze pressures and rectal compliance and sensation will be evaluated before and after randomization to alfuzosin (2.5 mg oral) or placebo (Figure 1) in the Charlton 7 CRU. During each epoch (i.e., baseline or drug), pressures will be evaluated before and after patients are randomized to one of 6 sequences (orders) of 3 interventions (i.e., 2 stressors and active relaxation). The same stressor/relaxation sequence will be applied during pre-drug and post drug epochs. Anorectal assessments, which will be performed with standard techniques, include:
- Anal resting and squeeze pressures using high resolution manometry, similar to the procedure employed in the clinical lab and in recent studies;
  - Rectal compliance and sensation using a barostat/ polyethylene balloon. A conditioning distention from 0-40 mmHg in 4 mm steps at 15 second intervals will be performed. Ten minutes thereafter, the balloon will be distended from 0-44 mmHg or maximum tolerated pressure in 4 mmHg steps; sensory thresholds for first sensation, desire to defecate, and urgency will be recorded
  - Rectal ramp distention. Because the contractile response to distention is influenced by the rate of distention, a ramp distention to 200 mL over 1 minute will be performed; this will be sustained for 2 minutes. While (ii) is useful for characterizing quasi-static pressure-volume relationships representing colonic tone, ramp distentions can uncover the active contractile response to distention.
  - Rectal sinusoidal oscillation will be performed at 5 cpm for 20 minutes after distention to 125 mL. This paradigm is more sensitive than barostat-driven distentions for uncovering increased rectal stiffness in fecal incontinence but has not been evaluated in constipation

**Figure 1. Experimental Design for Anorectal Study.** During the stress/relaxation epoch, subjects will receive 2 stress and 1 relaxation intervention in randomized order. The duration of this epoch includes two 10 minute rest periods between the 3 interventions. The manometry catheter will be removed and limited ambulation will be permitted while we are waiting for drug concentrations to increase. Combined, this wait period and the second equilibration period are 70 minutes long, which is within the range of  $t_{max}$  for alfuzosin (1.1 – 1.5 hours). PAT = peripheral arterial tonometry

- v. Rectal balloon expulsion will also be assessed in the seated position to confirm presence (or absence) of an evacuation disorder.
- b) Mental stressors and relaxation method. The mental stress testing protocol will be administered under the supervision of a licensed clinical psychologist who is familiar with these tests and routinely administers the same. Two stress interventions and a relaxation protocol will be provided in randomized order with 10-minute equilibration periods. Two different mental stress tasks of 6-minute duration will be performed. Each test is designed to address a different mental skill set. This was designed specifically to prevent mental fatigue and keep subjects motivated. All tasks will have intra-test levels of varying difficulty and will be externally paced, with the goal of stressing subjects as much as tolerated as judged by the psychologist administering the tests. It is known that external task pacing accentuates the induced mental stress. The aim is to keep subjects engaged and focused. The tasks, which will be performed in randomized order are as follows:
- i. A computerized version of the Stroop word-color conflict. Stroop word-color conflict test consists of three colored words (red, blue, and green) displayed in random order on a computer screen. Each word could appear in either its own color (visually concordant), or in one of the other 2 colors (visually discordant). The subject's task will be to enunciate the color of the word, not the actual word itself. A rectangular box will surround the stimulus color-word, and this task will also be externally paced, with the subject having to keep pace with the advancing box.
  - ii. Number subtraction of increasing difficulty (1 digit from 2 digits up to 3 digits from 3 digits) testing math skills.
  - iii. Relaxation will be induced by asking patients to view a CD obtained from Mayo Patient education. In essence, this CD encourages patients to close their eyes, be comfortable, monitor their breathing, and relax the entire body.  
Before and at the end of each task, subjects will be asked to rate their stress and arousal on four 10 mm long visual analog scales labeled tired-energetic, peaceful-tense, worried-relaxed, and active-drowsy.
- c) Blood pressure and heart rate measurements will be taken 30 seconds before, 2 minutes into, and at the end of each 6-minute mental stress task. Subjects will have 5-minute baseline rest periods between each mental stress task, during which they will be instructed to relax. At the end of the mental stress tasks, the reactive hyperemia protocol will be repeated. Double product will be calculated as systolic blood pressure multiplied by heart rate.
- d) Peripheral arterial tonometry (PAT) will provide an independent biological marker of mental stress, which causes vasoconstriction, and the  $\alpha_1$  antagonist, which causes vasodilatation. There is a characteristic PAT signal response to mental stress, with diminution of the signal amplitude during stress. A ratio of the stress PAT amplitude to baseline PAT amplitude (PAT score) of 0.8 or less is considered a positive response to mental stress and considered a marker for future stress-related cardiovascular events.

e) Drugs. After carefully reviewing the pharmacokinetic properties and side effects of all  $\alpha_1$  adrenoreceptor antagonists, we have opted to use alfuzosin, because it (i) is highly selective for urological tissues relative to the vascular system, (ii) has a low risk of orthostatic hypotension and (iii) penetrates the brain poorly. For example, in isolated human tissues, alfuzosin displays the highest selectivity ratio for the prostate over the vascular tissue (ratio, 144) compared with tamsulosin (90), doxazosin (51), and terazosin (19). In experimental animal models, the primary effect of alfuzosin is a urethral relaxant activity and not an antihypertensive effect. Administered intravenously to conscious normotensive rats at doses 3 to 10 times higher than those necessary to induce significant urethral relaxation, alfuzosin displays the lowest hypotensive activity compared with doxazosin, terazosin, and tamsulosin.

Alfuzosin (2.5 mg) has a mean bioavailability of 64%,  $t_{max}$  of 1.0 – 1.5 hours and a terminal  $t_{half}$  of 3-5 hours. The drug is extensively metabolized by the liver with only 11% of the administered dose excreted unchanged in the urine. This immediate release formulation, which is also manufactured by Sanofi-Aventis, not approved in the US but widely available in other countries, will be imported from UK (Xatral™, 2.5 mg) under an investigator-initiated IND (117098) from the FDA because the long  $t_{max}$  for alfuzosin ER limits its use in this acute study.

f) Stool collection. Using stool kits and standardized instructions, patients will collect stool samples according to the procedure in the Appendix. Stool samples will be frozen and stored in a -20°C freezer. The first stool specimen will be collected (a) without a laxative in controls and (b) if necessary, after their usual laxative regimen in patients. In Part B, the effects of alfuzosin extended-release (10 mg, Uroxatral) on bowel

symptoms will be evaluated. Since such use satisfies the requirements of 21 CFR 312.2 (b) (1), an IND is not required. We confirm that all the following apply to Part B of this study:

a) The investigation is not intended to be reported to FDA as a well-controlled study in support of a new indication for use nor intended to be used to support any other significant change in the labeling for the drug; and

b) The investigation is not intended to support a significant change in the advertising for the product; and

c) The investigation does not involve a route of administration or dosage level or use in a patient population or other factor that significantly increases the risks (or decreases the acceptability of the risks) associated with the use of the drug product; and

d) The investigation will be conducted in compliance with the requirements for institutional review set forth in 21 CFR 56 Institutional Review Boards and with the requirements for informed consent set forth in part 21 CFR 50 Protection of Human Subjects; and

e) The investigation will be conducted in compliance with the requirements of 21 CFR 312.7 - Promotion of Investigational Drugs.

f) Genome wide DNA analysis. Towards our long-term objective of uncovering associations between SNPs and DD, we propose to extract DNA from 10 ml of blood, to be drawn from study participants. DNA extraction will be conducted at the BAP Lab. Genome-wide analysis will be conducted using Illumina 610 QUAD microarray or

comparable approaches. Genotype-phenotype correlations will be examined using these patients and other patients in ongoing studies.

g) **Sequencing and analytical methods.** Using resources available in the UIUC-Mayo consortium, two complementary approaches will be utilized to analyze stool specimens from each subject. First, microbial DNA will be extracted from stool and tissue samples using standardized methods [33]. Phylotype profiles of the microbiome from control and constipated populations will be generated using deep rDNA hypervariable tag sequencing of the hypervariable V3-V5 region of the SSU rRNA gene, which has been validated for use with human microbiomes and is one of the methods of choice for the HMP. With the longer reads from the MiSeq (250x250 paired end reads), our sequencing will include both the V3-V5 RGTs making for a more optimal phylogenetic analysis [34]. Phylotype profiles of the mucosa-associated microbiome will be generated using rDNA sequencing of the hypervariable V3-V5 region, which has been validated for standard use by the human microbiome project. The 300 base pair reads will ensure a better optimal phylogenetic identification. Barcoding samples prior to sequencing will yield approximately 20,000 reads/sample, ensuring detection of both dominant (core microbiome) and poorly represented taxa (variable microbiome). Identifying the existent taxa, diversity, and ecological relationships within each sample requires that we process large volumes of 16S DNA sequence data. In order to accomplish this task we will follow protocols that we have quantitatively shown to be optimal. Paired end reads will be stitched, aligned, and classified using a custom pipeline (TORNADO v2.0).[35] Briefly, low base quality reads will be either trimmed or discarded,[36] and these reads will not be classified as a bacteria kingdom[37] or matched to the bacteria 16S rRNA secondary structure.[38] To evaluate the microbial diversity and abundance, UPARSE will be used for Operational Taxonomical Units (OTU) clustering,[39] and FastTree for phylogeny.[40] The 16S data will be clustered into OTUs at 97% sequence similarity, and the taxonomy will be assigned using the Ribosomal Database Project classifier. h) Effects of alfuzosin in bowel habits (Part B). During the first 2 weeks, bowel habits will be recorded at baseline. During the next 2 weeks, patients will be treated (double-blind) with placebo or alfuzosin (10 mg) ER once daily, which is FDA-approved dose for urinary symptoms. Symptom assessments are shown in Table 1 and in Appendices 1-5. Per eligibility criteria, subjects will discontinue medications which can affect GI transit during the baseline and treatment periods. Patients who need rescue medication, after three full days without a bowel movement, can receive 1-2 bisacodyl 5 mg tabs or a bisacodyl suppository (10 mg) or up to Fleet's enemas. In addition, patients who need relief of mild pain can use analgesic drugs such as NSAIDs and COX-2 inhibitors for up to two doses per week. During the procedure, intake of acetaminophen up to 1.5g per day in divided doses will be permissible.
